9.2 Study completion and post-study treatment

Study completion is defined as when the last subject finishes her/his EOS visit and any repeat assessments associated with this visit have been documented and followed-up appropriately by the investigator or, in the event of an early study termination decision, the date of that decision. Each subject will be required to complete the study in its entirety and thereafter no further study treatment will be made available to them.

All treated subjects should have a safety follow-up call conducted 30 days after end of treatment period (week 28), followed by post-treatment follow visits at week 37 and week 53. The information collected will be kept as source documentation. All SAEs reported during this time period must be reported as described in [Section 10.1.3](#) and SOM. Documentation of attempts to contact the subject should be recorded in the source documentation.

Continuing care should be provided by the investigator and/or referring physician after the EOS visit as per local standard of care.

10 Safety monitoring and reporting

10.1 Definition of adverse events and reporting requirements

10.1.1 Adverse events

An adverse event (AE) is any untoward medical occurrence (e.g. any unfavorable and unintended sign [including abnormal laboratory findings], symptom or disease) in a subject or clinical investigation subject after providing written informed consent for participation in the study. Therefore, an AE may or may not be temporally or causally associated with the use of a medicinal (investigational) product.

The investigator has the responsibility for managing the safety of individual subject and identifying adverse events.

Novartis qualified medical personnel will be readily available to advise on trial related medical questions or problems.

The occurrence of adverse events must be sought by non-directive questioning of the subject at each visit during the study. Adverse events also may be detected when they are volunteered by the subject during or between visits or through physical examination findings, laboratory test findings, or other assessments.

Adverse events must be recorded under the signs, symptoms, or diagnosis associated with them, accompanied by the following information (as far as possible) (if the event is serious refer to [Section 10.1.2](#)):

1. The severity grade
 - mild: usually transient in nature and generally not interfering with normal activities
 - moderate: sufficiently discomforting to interfere with normal activities
 - severe: prevents normal activities
2. its relationship to the study treatment . If the event is due to lack of efficacy or progression of underlying illness (i.e. progression of the study indication) the assessment of causality will usually be 'Not suspected.' The rationale for this guidance is that the symptoms of a lack of efficacy or progression of underlying illness are not caused by the trial drug, they happen in spite of its administration and/or both lack of efficacy and progression of underlying disease can only be evaluated meaningfully by an analysis of cohorts, not on a single subject
3. its duration (start and end dates) or if the event is ongoing, an outcome of not recovered/not resolved must be reported
4. whether it constitutes a SAE (see [Section 10.1.2](#) for definition of SAE) and which seriousness criteria have been met
5. action taken regarding with study treatment

All adverse events must be treated appropriately. Treatment may include one or more of the following:

- Dose not changed
- Dose Reduced/increased
- Drug interrupted/withdrawn

6. its outcome: not recovered/not resolved; recovered/resolved; recovered/resolved with sequelae; fatal; or unknown

Conditions that were already present at the time of informed consent should be recorded in medical history of the subject.

Adverse events (including lab abnormalities that constitute AEs) should be described using a diagnosis whenever possible, rather than individual underlying signs and symptoms.

Adverse event monitoring should be continued for at least 30 days (or 5 half-lives or end of study visit, whichever is longer) following the last dose of study treatment.

Information about adverse drug reactions for the investigational drug can be found in the IB.

Abnormal laboratory values or test results constitute adverse events only if they fulfill at least one of the following criteria:

- they induce clinical signs or symptoms
- they are considered clinically significant
- they require therapy

Clinically significant abnormal laboratory values or test results must be identified through a review of values outside of normal ranges/clinically notable ranges, significant changes from baseline or the previous visit, or values which are considered to be non-typical in subjects with the underlying disease.

Follow the instructions found in the Site Operations Manual for data capture methodology regarding AE collection for subjects that fail screening.

10.1.2 Serious adverse events

An SAE is defined as any adverse event [appearance of (or worsening of any pre-existing)] undesirable sign(s), symptom(s), or medical condition(s) which meets any one of the following criteria:

- fatal
- life-threatening

Life-threatening in the context of a SAE refers to a reaction in which the subject was at risk of death at the time of the reaction; it does not refer to a reaction that hypothetically might have caused death if it were more severe (please refer to the ICH-E2D Guidelines).

- results in persistent or significant disability/incapacity
- constitutes a congenital anomaly/birth defect
- requires inpatient hospitalization or prolongation of existing hospitalization, unless hospitalization is for:
 - routine treatment or monitoring of the studied indication, not associated with any deterioration in condition
 - elective or pre-planned treatment for a pre-existing condition that is unrelated to the indication under study and has not worsened since signing the informed consent
 - social reasons and respite care in the absence of any deterioration in the subject's general condition

- treatment on an emergency outpatient basis for an event not fulfilling any of the definitions of a SAE given above and not resulting in hospital admission
- is medically significant, e.g. defined as an event that jeopardizes the subject or may require medical or surgical intervention to prevent one of the outcomes listed above

Medical and scientific judgment should be exercised in deciding whether other situations should be considered serious reactions, such as important medical events that might not be immediately life threatening or result in death or hospitalization but might jeopardize the subject or might require intervention to prevent one of the other outcomes listed above. Such events should be considered as “medically significant.” Examples of such events are intensive treatment in an emergency room or at home for allergic bronchospasm, blood dyscrasias, or convulsions that do not result in hospitalization or development of dependency or abuse (please refer to the ICH-E2D Guidelines).

All malignant neoplasms will be assessed as serious under “medically significant” if other seriousness criteria are not met and the malignant neoplasm is not a disease progression of the study indication.

Any suspected transmission via a medicinal product of an infectious agent is also considered a serious adverse reaction.

All reports of intentional misuse and abuse of the product are also considered serious adverse event irrespective if a clinical event has occurred.

10.1.3 SAE reporting

To ensure subject safety, every SAE, regardless of causality, occurring after the subject has provided informed consent and until 30 days after the last study visit must be reported to sponsor safety within 24 hours of learning of its occurrence. Detailed instructions regarding the submission process and requirements are to be found in the investigator folder provided to each site.

Screen Failures

SAEs occurring after the subject has provided informed consent until the time the subject is deemed a Screen Failure must be reported to sponsor.

Definition of Run-In Failures

A subject who is screened but not randomized/treated after the run-in period. SAEs collected between time subject signs ICF until time that subject is determined to be a run-in failure.

Definition of Baseline Failures

A subject who performs baseline assessments but not randomized/treated after baseline visit. SAEs collected between time subject signs ICF until time that subject is determined to be a baseline failure.

Randomized

SAEs collected between time subject signs ICF until 30 days after the subject has discontinued study treatment or completed their last study visit.

All follow-up information for the SAE including information on complications, progression of the initial SAE and recurrent episodes must be reported as follow-up to the original episode within 24 hours of the investigator receiving the follow-up information. An SAE occurring at a different time interval or otherwise considered completely unrelated to a previously reported one must be reported separately as a new event.

If the SAE is not previously documented in the Investigator's Brochure or Package Insert (new occurrence) and is thought to be related to the study treatment, a CMO & PS Department associate may urgently require further information from the investigator for health authority reporting. Novartis may need to issue an Investigator Notification (IN) to inform all investigators involved in any study with the same study treatment that this SAE has been reported.

Suspected Unexpected Serious Adverse Reactions (SUSARs) will be collected and reported to the competent authorities and relevant ethics committees in accordance with EU Guidance 2011/C 172/01 or as per national regulatory requirements in participating countries.

Any SAEs experienced after the 30 day period after the last study visit should only be reported to sponsor Safety if the investigator suspects a causal relationship to study treatment.

10.1.4 Pregnancy reporting

Pregnancies

To ensure subject safety, each pregnancy occurring after signing the informed consent must be reported to Novartis within 24 hours of learning of its occurrence. The pregnancy should be followed up to determine outcome, including spontaneous or voluntary termination, details of the birth, and the presence or absence of any birth defects, congenital abnormalities, or maternal and/or newborn complications.

Pregnancy should be recorded and reported by the investigator to the Novartis Chief Medical Office and Patient Safety (CMO&PS). Pregnancy follow-up should be recorded on the same form and should include an assessment of the possible relationship to the investigational treatment any pregnancy outcome. Any SAE experienced during pregnancy must be reported.

10.1.5 Reporting of study treatment errors including misuse/abuse

Medication errors are unintentional errors in the prescribing, dispensing, administration or monitoring of a medicine while under the control of a healthcare professional, subject or consumer (EMA definition).

Misuse refers to situations where the medicinal product is intentionally and inappropriately used not in accordance with the protocol.

Abuse corresponds to the persistent or sporadic, intentional excessive use of a medicinal product, which is accompanied by harmful physical or psychological effects.

Study treatment errors and uses outside of what is foreseen in the protocol will be recorded on the appropriate CRF irrespective of whether or not associated with an AE/SAE and reported to Safety only if associated with an SAE. Misuse or abuse will be collected and reported in the safety database irrespective of it being associated with an AE/SAE within 24 hours of investigator's awareness.

Table 10-1 Guidance for capturing the study treatment errors including misuse/abuse

Treatment error type	Document in Dosing CRF (Yes/No)	Document in AE eCRF	Complete SAE form
Unintentional study treatment error	Yes	Only if associated with an AE	Only if associated with an SAE
Misuse/Abuse	Yes	Yes	Yes, even if not associated with a SAE

For more information on AE and SAE definition and reporting requirements, please see the respective sections.

10.2 Additional Safety Monitoring

10.2.1 Liver safety monitoring

To ensure subject safety and enhance reliability in determining the hepatotoxic potential of an investigational drug, a standardized process for identification, monitoring and evaluation of liver events has to be followed.

The following two categories of abnormalities / adverse events have to be considered during the course of the study (irrespective of whether classified/reported as AE/SAE):

- Liver laboratory triggers, which will require repeated assessments of the abnormal laboratory parameter
- Liver events, which will require close observation, follow-up monitoring and contributing factors are recorded on the appropriate CRFs

Please refer to [Table 16-1](#) in [Section 16.1](#) for complete definitions of liver laboratory triggers and liver events.

Every liver event defined in [Table 16-1](#) should be followed up by the investigator or designated personnel at the trial site, as summarized below. Additional details on actions required in case of liver events are outlined in [Table 16-2](#). Repeat liver chemistry tests (i.e. ALT, AST, TBL, PT/INR, ALP and G-GT) to confirm elevation.

- These liver chemistry repeats will be performed using the central laboratory. If results will not be available from the central laboratory, then the repeats can also be performed at a local laboratory to monitor the safety of the subject. If a liver event is subsequently reported, any local liver chemistry tests previously conducted that are associated with this event should have results recorded on the appropriate CRF.
- If the initial elevation is confirmed, close observation of the subject will be initiated, including consideration of treatment interruption if deemed appropriate.

- Discontinuation of the investigational drug (refer to the Discontinuation of study treatment section , [Section 9.1.1](#)), if appropriate
- Hospitalization of the subject if appropriate
- Causality assessment of the liver event
- Thorough follow-up of the liver event should include
 - These investigations can include based on investigator's discretion: serology tests, imaging and pathology assessments, hepatologist's consultancy; obtaining more detailed history of symptoms and prior or concurrent diseases, history of concomitant drug use, exclusion of underlying liver disease

All follow-up information and procedures performed must be recorded as appropriate in the CRF.

Refer to the SOM for additional details.

10.2.2 Renal safety monitoring

Renal safety monitoring is already performed as part of the study endpoints.

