4.5.6 Risk mitigation strategy

Commercially Confidential Information

There are CCI potential risks that have been identified
namely 'infections,'

Commercially Confidential Information

The former is mitigated by vaccinations against encapsulated
bacteria as described in [Section 4.5.3](#).

Commercially Confidential Information

Patients will return to the clinic on a regular basis. During these visits safety, tolerability, efficacy and PK/PD data will be collected. Standard safety assessments will include vital signs, physical examinations, ECG, clinical laboratory evaluations (hematology, blood chemistry and urinalysis), and AEs as outlined in the Assessment schedule ([Table 8-1](#) and [Table 8-2](#)). In addition to standard clinical laboratory assessments, subjects will be monitored regularly for

signs and symptoms of infections, Commercially Confidential Information

will be informed to report any symptoms to the clinical staff to assure proper assessment and so that care can be administered in a timely manner.

For patients in the rituximab arm, sites will be asked to follow local guidelines for administration of the i.v. infusion, including the rate of administration, use of premedication, frequency of observation of vital signs and monitoring for evidence of infusion reactions.

Clinical laboratory evaluations and standard safety assessments will be performed per the Assessment Schedule ([Table 8-1](#) and [Table 8-2](#)) to monitor for signs and symptoms of adverse events.

In agreement with the primary and secondary objectives, measurement of UPCR CCI , 24-h urine excretion of albumin and protein will be made, and changes in renal function will be assessed via serum creatinine and estimated glomerular filtration rate (eGFR, Chronic Kidney Disease - Improved Prediction Equations (CKD-EPI)).

Commercially Confidential Information

A priori defined stopping criteria and guidelines ([Section 9.1.4](#)) in addition to the clinical opinion of the investigator will be used to protect individual patient safety during the trial.

COVID-19 specific risk mitigation strategies ([Section 8.4.6](#)) were implemented in this study as part of the clinical study procedures. Finally, key safety data will be reviewed by the sponsor on an ongoing basis.

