Adverse events which will be counted for a specific treatment period are those which are treatment-emergent. These events are those with an onset after the start of the treatment period, or which were present prior to the start of the treatment period but increased in severity, changed from being not suspected to being suspected of study drug relationship, or developed into SAEs after the start of the treatment period.

Heatmaps will be provided by treatment group displaying the on- and off-set of the most severe AE in a subject over time.

Vital signs

Summary statistics will be provided on all vital signs data by treatment and visit/time.

12-lead ECG

PR, QRS, QT, QTcF, and RR intervals will be obtained from 12-lead ECGs for each subject during the study. ECG data will be read and interpreted (locally). Summary statistics will be provided on all ECG data by treatment and visit/time.

Clinical laboratory evaluations

Summary statistics will be provided on all laboratory data by treatment and visit/time. Shift tables using the low/normal/high/ (low and high) classification will be used to compare baseline to the worst on-treatment value.

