## **6 Statistical methods for Pharmacodynamic (PD) parameters**

All subjects within the PD analysis set      Commercially Confidential Information  
will be included in the PD data analysis.

Unless otherwise stated, summary statistics of continuous data will include n, mean (arithmetic and geometric), SD, CV (arithmetic and geometric), median, minimum and maximum, as appropriate, while categorical data will be summarized as frequencies and percentages.

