### **6.2.2 Descriptive analyses**

The secondary PD variables will be listed by treatment, subject, and visit/sampling time. For the continuous variables change from baseline or ratio to baseline will be provided as deemed relevant. Summary statistics will be provided by treatment and visit/time for raw values and change from baseline or ratio to baseline as deemed relevant.

Graphical methods may be employed for the continuous variables to show group and individual summary plots over time by treatment.

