#### eGFR change from baseline

Summary statistics for the change from baseline to 24 weeks in eGFR (applying the Chronic Kidney Disease Epidemiology Collaboration, CKD-EPI, equation) will be provided by treatment.

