## **Clinical laboratory evaluations**

All laboratory data will be listed by treatment group, subject, and visit/time and if normal ranges are available abnormalities will be flagged. Abnormal laboratory values of potential clinical importance will be listed in a separate listing by treatment, subject, and visit/time. Pregnancy test results for women will also be listed in a separate listing by treatment group, subject, and visit/time. Shift tables using the low/normal/high/(low and high) classification will be used to compare baseline to the worst on-treatment value. Summary statistics will be provided by treatment and visit/time.

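### The creatinine shift table cannot register worsening in a subject already high at baseline, and no objective by-arm count of large eGFR falls is visible

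*Protocol*

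**What the plan says.** Protocol 10.2.2 is a single sentence: "Renal safety monitoring is already performed as part of the study endpoints". Protocol 4.5.6 adds that "changes in renal function will be assessed via serum creatinine and estimated glomerular filtration rate".

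The renal-function endpoint is reported as "Summary statistics for the change from baseline to 24 weeks in eGFR", by treatment (SAP 6.2.2). For the continuous secondary variables in general, the same section adds: "Summary statistics will be provided by treatment and visit/time for raw values and change from baseline or ratio to baseline as deemed relevant". SAP section 6 sets the content of these summaries, which includes "SD, CV (arithmetic and geometric), median, minimum and maximum, as appropriate".

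For laboratory data, SAP 7.2 plans: "Shift tables using the low/normal/high/(low and high) classification will be used to compare baseline to the worst on-treatment value". Protocol 12.5.2 says the same. SAP 7.2 also plans summary statistics by visit, full listings and a further listing: "Abnormal laboratory values of potential clinical importance will be listed in a separate listing by treatment, subject, and visit/time". SAP 7.3 adds boxplots of laboratory parameters over time.

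Inclusion criterion 7 sets an eGFR floor of 30 mL/min per 1.73 m² at screening. Tables 8-1 and 8-2 schedule eGFR at every on-site treatment visit in both arms.

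**The concern.** Progressive loss of renal function is the main long-term harm of this disease (Protocol 1.2), and the trial sets a new drug against rituximab. A reader of the study report will want to know how many subjects in each arm had a large fall in eGFR on treatment.

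Of the visible laboratory tables, only the shift table takes each subject's worst value across visits and counts subjects by arm. It measures against the normal range, not against the subject's own baseline. For creatinine in this population that is a weak yardstick: a subject already above range has no higher category to move to, and a subject well within range can lose much function before leaving it. At stake is whether the two arms can be compared on large renal decline by a fixed rule.

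**Working it through.** The documents state no figure to reproduce here. The check is on what each planned output can show.

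**1. Shift cell.** Let baseline creatinine be b times the upper limit of normal (ULN), rising m-fold. The category is high if the value exceeds 1 × ULN. With b = 1.05, 1.2, 1.5, 2.0 and m = 1.5, 2, 3 (assumed), b × m > 1 in all 12 cases, so every one is high to high. This is general: b > 1 and m > 1 always give b × m > 1.

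In eGFR terms, the documents name CKD-EPI but give neither its version nor a creatinine limit. Assume the 2009 equation, and a ULN of 1.2 to 1.3 mg/dL in men and 1.0 to 1.1 in women. At ages 45 to 65, creatinine is then already high below an eGFR of about 57 to 73 in men and 53 to 68 in women. For a man of 55:
- Creatinine 1.4 to 2.8 mg/dL is eGFR 56 to 24, a fall of (56 − 24)/56 = 57%. The shift is high to high.
- Creatinine 0.8 to 1.2 mg/dL is eGFR 101 to 68, a fall of (101 − 68)/101 = 33%. The shift is normal to normal.

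**2. Mean change.** If k of n subjects each lose half of a baseline eGFR B, the arm mean moves by −k × (B/2)/n. With n = 24 (Protocol 12.8.1):

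| B | k = 1 | k = 2 |
|---|---|---|
| 30 | −15/24 = −0.6 | −1.25 |
| 40 | −20/24 = −0.8 | −1.7 |
| 60 | −30/24 = −1.25 | −2.5 |

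For an assumed SD of change of 8 to 15, the standard error of an arm mean is SD/√24 = 1.6 to 3.1. The mean alone would not reveal one such subject.

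**3. Minimum.** The planned minimum change would show that arm's largest loss at that visit (at least 15, 20 or 30 in these cases). It would not show how many subjects had such a loss, each subject's worst value across visits, or whether the fall persisted.

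**4. The outputs side by side.**

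| Output | Relative to own baseline | Worst value across visits | Counts subjects by arm |
|---|---|---|---|
| eGFR change at week 24 | yes | no | no |
| Summaries by visit | where deemed relevant | no | no |
| Shift table | range category only | yes | yes |
| Boxplots | not stated | no | no |
| Listings | not stated | by reading through | no |
| AE tables | by clinical review | not applicable | yes, on judgement |

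No row combines own baseline, worst value and a count by a fixed rule. SAP 7.2 does give a number and percentage by treatment for notable ECG values.

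**5. Would a count be informative at this size?** The chance of at least one counted subject is 1 − (1 − p)^n. For assumed true rates p of 2%, 5%, 10% and 15%, it is 38%, 71%, 92% and 98% with n = 24, and 33%, 64%, 88% and 96% with n = 20. The documents give no rates.

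**The case against.** A reader might infer that sharp renal decline is not counted by arm at all. The documents do not support that. Protocol 8.4.1 requires every abnormal laboratory result to be assessed against the adverse event criteria. Protocol 10.1.1 extends the review to significant changes from baseline or from the previous visit, which reaches both blind spots of the shift table. Adverse events are then counted by arm, by system organ class, preferred term and severity.

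A reader might also infer that the report could show no renal signal. That goes too far as well: with about 24 subjects per arm, the minima, boxplots and listings would expose an individual with a large fall.

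Section 10.2.2 concerns monitoring during conduct and promises nothing about tabulation. Parts of the SAP, and text after the laboratory table in Protocol 8.4.1, are redacted, so absence from the full plan cannot be proved. The study is a non-confirmatory proof of concept, and counts could be derived later from listed data.

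All of this stands, but it does not supply an objective count. The adverse event route turns on what each investigator considers clinically significant, in an open-label trial with no data monitoring committee. A count derived after the data are seen would use a threshold chosen with knowledge of the results.

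**Conclusion.** The point holds as a cheap improvement. For creatinine, the shift table cannot show worsening in a subject already high at baseline, or a large rise within the normal range. The unredacted text shows no threshold-based count by arm of subjects with a large on-treatment fall in eGFR.

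The first statement follows from the definition of the categories and needs no outside figure. The eGFR equivalents rest on an assumed equation version and assumed creatinine limits, and the comparison with the standard error rests on an assumed SD of change. It would be tempting to say that many subjects start with high creatinine. The eGFR floor of 30 shows only that they can; the documents give no distribution. Nothing here calls for a change to Section 10.2.2.

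**What to change.** In SAP 7.2, add one descriptive table by treatment on the safety set. It should give the number and percentage of subjects whose worst on-treatment eGFR, relative to their own baseline, crosses pre-set reporting categories, with matching categories for creatinine. Falls of at least 30% and at least 40% are examples; the sponsor sets the cut-offs before database lock. Add a column for falls confirmed at the next visit. A footnote should say how a fall first seen at Day 169 is handled, since the next scheduled eGFR is at Day 266, in follow-up, when local standard of care is permitted. State that these are reporting categories only, not monitoring or treatment rules.

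The cost is SAP wording and one extra table from data already collected. The downside is that transient dips will appear in the unconfirmed column.
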